# Evaluation of low-cost techniques for detecting sickle cell disease and $\beta$ -thalassemia in Nepal

# 1.0 Background

## 1.1 Sickle cell disease

Sickle cell disease (SCD) is a collection of inherited blood disorders, and is a multisystem disorder affecting nearly every organ in the body [1]. The disease primarily causes erythrocytes or red blood cells (RBCs) to be distorted and rigid due to polymerization (e.g. during deoxygenation), often changing them to crescent or sickle shaped cells [2]. Other cascading effects include hemolytic anemia, blockage of microvasculature (capillaries and small blood vessels), episodes of acute illness (such as vaso-occlusive pain crisis or sickle cell crisis), and progressive organ damage [3], [4]. The chances of survival and quality of life drastically increase with early diagnosis, newborn screening, penicillin prophylaxis, pneumococcal immunization, blood transfusion, hydroxyurea treatment, hematopoietic stem-cell transplantation, and education about disease severity and complications [1], [4].

SCD is one of the most common monogenic diseases worldwide and results from mutations in the  $\beta$ -globin gene [1], [3]. The most common and severe form of SCD is sickle cell anemia (SCA), caused by the inheritance of  $\beta^S$  alleles or the variant HbS (hemoglobin S or sickle hemoglobin) genes from both parents – resulting in the homozygous form HbSS, instead of the normal homozygous form HbAA. Another form of SCA is HbS/ $\beta^0$  thalassemia, caused by the inheritance of a  $\beta^0$  thalassemia mutation from one parent and an HbS gene from another, resulting in no normal HbA and a majority of HbS. The heterozygous form HbAS, known as sickle cell trait (SCT), affects millions of people worldwide and is usually not associated with hematological abnormalities [2]. On the other hand, compound heterozygous conditions are associated with mild to severe clinical courses and are also categorized as SCD. Some compound heterozygous conditions include HbS with hemoglobin C or HbC (HbSC), HbS with  $\beta$ -thalassemia (HbS/ $\beta^0$ -thalassemia or HbS/ $\beta^+$ -thalassemia), and HbS with other  $\beta$  globin variants (e.g. HbSD and HbSOArab) [1], [3], [4].

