## 6.3 Statistical Analysis Plan

Considering HPLC as the reference test, the sensitivity, specificity, positive predictive value (PPV) and negative predictive value (NPV) of the index tests or low-cost techniques (automated

sickling test, HbS solubility test, HemoTypeSC, Sickle SCAN, and Gazelle Hb variant test) will be evaluated.

For each case, the following definitions apply:

- True positive (TP): indicates a positive result for both the index test and the reference test
- True negative (TN): indicates a negative result for both the index test and the reference test
- False positive (FP): indicates a positive result for the index test, but a negative result for the reference test
- False negative (FN): indicates a negative result for the index test, but a positive result for the reference test

The following metrics will be calculated using the total number of TP, TN, FP, and FN:

Sensitivity = 
$$\frac{TP}{TP + FN} \times 100\%$$
  
Specificity =  $\frac{TN}{FP + TN} \times 100\%$   
 $PPV = \frac{TP}{TP + FP} \times 100\%$   
 $NPV = \frac{TN}{TN + FN} \times 100\%$ 

The metrics (sensitivity, specificity, PPV, and NPV) for the index tests will be calculated for the following two categories:

- 1. **Detection analysis by hemoglobin variant** (HbA, HbS, HbC, β-thalassemia): Heterozygous or homozygous forms containing a particular hemoglobin variant in both the index test and the reference test are true positive results for that variant. Test results lacking a particular hemoglobin variant in both index and reference tests, irrespective of other variants present, are true negative results for that variant. The following hemoglobin variants will be analyzed for the index tests.
  - HbS Solubility: HbA, HbS
  - Automated sickling: HbA, HbS
  - HemoTypeSC: HbA, HbS, HbC
  - Sickle SCAN: HbA. HbS. HbC
  - Gazelle Hb Variant: HbA, HbS, HbC, β-thalassemia
- 2. **Detection analysis by phenotype**: In this analysis, the metrics for homozygous and heterozygous states will be calculated differently. The following phenotypes will be analyzed for the index tests.
  - Automated sickling: HbAA, HbAS, HbSS, Overall
  - HemoTypeSC: HbAA, HbAS, HbSS, (HbAC, HbSC, HbCC), Overall
  - Sickle SCAN: HbAA, HbAS, HbSS, (HbAC, HbSC, HbCC), Overall
  - Gazelle Hb Variant: HbAA, HbAS, HbSS, HbS/β-thalassemia, HbA/β-thalassemia, Hbβ/β-thalassemia, (HbAC, HbSC, HbCC), Overall

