#### Automated scanning using microscope

- Place microscope slide in slide holder of microscope unit (Octopi microscope)
- Identify the edges of the field of view for scanning
- Run program to automatically scan and capture images in the computer (translation of the stage and slide enabled by motors)
- Save images for machine learning algorithm (training/testing data set)

**Figure 1** | Blood film containing SCT blood mixed with 2% sodium metabisulphite, showing minimal sickle cells around 10 minutes after sample preparation (left) and increased number of sickle cells around 1.5 hours after sample preparation (right); 40x objective, 10x eyepiece

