# 7.8 Neural Network Training and Testing

Data manipulation and analysis will be done through Python. All software to be utilized is opensource and does not have commercial implications. In order to optimize the screening algorithm, multiple neural network configurations will be tested and compared. All the models tested for classification will use existing pre-trained models that have applications in image classification. In each case, the acquired images will be split into three groups, consisting of training data (around 80%), validation data, (around 10%) and testing data (around 10%). The data will be used to train the neural network using a pre-trained supervised machine learning model, whereby the images are input and the parameters of the network are optimized to classify images by hemoglobin phenotype. The test data will test the performance of the trained network on images that have not been used for training. We will use the neural networks most commonly used for medical image classification, such as EfficientNet, ResNeXt, ResNet-50, DenseNet, and Xception. When possible, training will occur locally on the laboratory computer at UBC. For networks that require additional computing power, UBC ARC Sockeye or Compute Canada will be used.

All the machine learning algorithms will only include de-identified data, such as images of blood films and hemoglobin phenotype (such as sickle cell trait or HbAS). Personal identifying information, such as participant names, will not be associated with any of the data used for analysis or stored online.

Cloud computing facilities, such as those from Compute Canada, will be utilized to train and test machine learning algorithms on the final dataset of images. Compute Canada is a cloud computing service provided by Digital Research Alliance of Canada (the Alliance) to Canadian research institutions. The servers and clusters (e.g. Cedar cluster located in BC) will be accessed using Secure Shell Protocol (SSH). For the analysis (before sharing the data publicly), de-identified images may be stored securely in UBC servers or in servers for Compute Canada.

The de-identified data (such as images of blood films and associated de-identified data like hemoglobin phenotype) will be deposited in an online public repository, such as Federated Research Data Repository.

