## 13. Limitations

Many SCD and  $\beta$ -thalassemia patients will be undergoing treatment and taking medications, which could potentially affect the interpretability of results of the sickling test. Nevertheless, blood films of patients with treatment are expected to include sickled cells during the sickling test. The analyses (e.g. machine learning training) will include information of whether or not patients have had treatment or medication, and any differences in results due to the treatment will be reported.

The population of patients in Nepalgunj are mostly of South Asian descent with possibly different haplotype than that of patients elsewhere (e.g. in Africa). This may have some

implications in differentiating SCD vs. SCT elsewhere, if the machine learning algorithm is only trained using a population of different haplotypes. To improve the accuracy of the machine learning classification, it may be required to add data from the population being tested.

In addition to the homozygous HbSS form of SCA, other heterozygous forms of  $\beta$ -thalassemia (with HbS) could lead to similar levels of sickling. It is unclear whether these can be differentiated in the sickling test. Additionally, the lateral flow assays (HemoTypeSC and Sickle SCAN) do not detect  $\beta$ -thalassemia.

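### Section 7.8 splits images with no rule that keeps a participant in one subset and no rule for one call per participant, so the automated sickling test's accuracy is liable to be inflated

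*Combined protocol and SAP*

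**What the plan says.** Section 7.8 (Neural Network Training and Testing) gives the partition: "the acquired images will be split into three groups, consisting of training data (around 80%), validation data, (around 10%) and testing data (around 10"%). In the same section "the parameters of the network are optimized to classify images by hemoglobin phenotype", and the only condition on the test set is: "The test data will test the performance of the trained network on images that have not been used for training".

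Section 7.5.1, under automated scanning, describes how the images arise: "Run program to automatically scan and capture images in the computer (translation of the stage and slide enabled by motors"), then "Save images for machine learning algorithm (training/testing data set"). A motorised scan of a slide implies more than one image per slide; the number is not given. Section 7.8 takes the ground truth for the images from HPLC, so all images of one participant share one label. Section 8.0 has the algorithms tested on the data collected in this study. No separate test cohort is named, and the Vancouver trials are not given that role.

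The claims are made about people or their samples. Hypothesis 2 concerns HbS detection in blood samples, Hypothesis 3 concerns classifying individuals with sensitivity above 90%, and section 6.3 sets an index-test result against a reference-test result. For the phenotype analysis section 6.3 lists "Automated sickling: HbAA, HbAS, HbSS, Overall". The only slide-level decision rule, more than 25% of cells sickled, is for manual observation.

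**The concern.** Images of one person can share slide preparation, focus, illumination and that person's cell morphology. If some of them are in training and others in testing, the network can score well on a test image partly because it has learned that slide. Image accuracy measured this way need not carry over to a person the network has never seen.

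Accuracy of the automated test is part of the primary endpoint, and suitability for deployment in rural Nepal is a secondary one (section 5.0). Both need accuracy in unseen people. The solubility and manual sickling tests have no training step, so any inflation would tilt Hypothesis 2 towards the automated test, and the reported sensitivity and specificity would not reveal it.

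The missing aggregation rule adds to this. Section 6.3 needs one index result per sample, while section 7.8 produces one output per image, and nothing links them. In the phenotype analysis there is also a labelling gap: half the planned sample belongs to the three β-thalassemia groups, which have no class in the list for this test.

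**Working it through.** **Inputs from the documents.** Six groups of about 20 participants, 6 × 20 = 120, which agrees with the stated total (sections 6.3 and 7.2.1). Split of images about 80/10/10 (section 7.8). The plan states no power or precision calculation for this test to reproduce.

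**Assumed, because not given.** Images per participant, m, and random allocation of images to subsets. Section 7.8 does not say that allocation is random; this is the literal reading with no grouping.

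**1. Share of test images whose person is also in training.** There are T = 120m images, of which h = 0.2T are outside training. For a given test image:

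P = 1 − C(h−1, m−1) / C(T−1, m−1), which is close to 1 − 0.2^(m−1).

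- m = 2: T = 240, h = 48; 1 − 47/239 = 80.3%
- m = 3: T = 360, h = 72; 1 − (71 × 70)/(359 × 358) = 96.1%
- m = 5: T = 600, h = 120; 99.85%

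If only the 60 HbAA, HbAS and HbSS participants were used, the figures would be 80.7%, 96.3% and 99.9%, so the result hardly depends on which set is imaged.

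**2. Expected number of unseen people in the test set.** These are people with no training image and at least one test image (people whose images are all in validation do not count):

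120 × [C(h, m) − C(h/2, m)] / C(T, m)

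- m = 2: 120 × (1128 − 276)/28680 = 3.6
- m = 3: 120 × (59640 − 7140)/7711320 = 0.8
- m = 5: 0.03

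From m = 3, fewer than one unseen person is expected in the test set.

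**3. From overlap to bias (illustration only).** Let p be true accuracy in new people, L the overlap share from step 1, and q the fraction of otherwise wrong overlapping images that come out right because the network recognises the slide. Apparent accuracy is p + (1 − p) × q × L. With p = 80% and L close to 1:

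- q = 0: 80%
- q = 0.25: 85%
- q = 0.5: 90%
- q = 1: 100%

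The documents give no information on q or p, so the bias may be nil or enough to reach the 90% target.

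**4. What a participant-level split leaves.** Ten percent of 120 is 12 test participants, 2 per category. Exact (Clopper-Pearson) 95% lower limits if every call is correct: 2/2, 15.8%; 12/12, 73.5%. If every participant receives one held-out call by cross-validation: 20/20 in a category, 83.2%; 60/60 (for example all HbS-positive), 94.0%.

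**5. Labels.** HbS is present by plan in HbSS, HbAS and HbS/β-thalassemia, 20 + 20 + 20 = 60, and absent in the other 60. For phenotype, 3 × 20 = 60 participants are outside HbAA, HbAS and HbSS. Of the sickle/β-thalassemia forms section 13 says "It is unclear whether these can be differentiated in the sickling test", while section 1.1 says "compound heterozygous conditions are associated with mild to severe clinical courses and are also categorized as SCD" and section 6.3 equates SCD with HbSS.

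**The case against.** The strongest reply is that section 7.8 is silent rather than wrong. It never says that allocation is random or that one person's images will be spread over subsets. A split grouped by participant would also be a split of the acquired images, and the team may intend one. This stands: a reader might infer that the plan has chosen to mix people across subsets, or that accuracy will be inflated, and the text supports neither. It remains true that the only stated safeguard concerns the image, and that the plan can be followed to the letter with almost every test image coming from a person already in training.

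It is also fair that overlap is not bias, and that the percentages rest on an assumed m. Section 6.3 gives an HbS definition that covers all 120 participants whatever other variants they carry, so the labelling gap is confined to the phenotype analysis and the training labels. Section 13 already discloses that the sickling test may not separate the compound forms.

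Two further inferences fail. One is that networks will be tuned on the test data: section 7.8 sets aside separate validation data, and nothing shows tuning on the test set. The other is that 20 per class lets Hypothesis 3 be met only as a point estimate. The hypothesis does not say that it is judged class by class and sets no confidence-limit criterion, and section 6.3 also lists an overall metric. Pooled over 60 participants, 60/60 has a lower limit of 94.0% and 59/60 of 91.1%.

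Finally, the other index tests and Hypothesis 1 are untouched, and section 7.8 says that the algorithm will not diagnose new patients. That limits the scope but does not remove the point.

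**Conclusion.** The concern holds as a gap in the plan with a predictable direction of bias. The unit of splitting and classification is the image, the claims are about people or samples, and nothing connects the two. The accuracy of the automated sickling test is liable to be overstated for Hypotheses 2 and 3, and any overstatement favours it in the Hypothesis 2 comparison. The size cannot be computed and may be zero. What can be shown, given random image allocation and an assumed 2, 3 or 5 images per person, is an overlap of 80%, 96% or 99.9% of test images. If there were exactly one image per participant the overlap would vanish, but the scanning procedure points the other way. This should be settled before the networks are trained, because it bears on a primary endpoint and the published accuracy figures would not show the problem.

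**What to change.** 1. In section 7.8, assign images to training, validation and test sets by the unique participant code, so that all images of one participant stay in one subset. Section 7.4 already ties images to these codes.
2. Pre-state one rule that turns a participant's image outputs into one call, for example averaging class probabilities over that person's images and taking the highest. In section 6.3, compute this test's metrics once per participant, only from calls on held-out participants.
3. Cross-validation grouped by participant is one suitable way to do this, since a 10% participant hold-out leaves about 12 people, about 2 per category. It gives every participant one held-out call.
4. Leave HbS detection in all 120 as section 6.3 defines it. For the phenotype analysis, state how participants in the three β-thalassemia groups are labelled in training and which call counts as correct for them, or limit that analysis to HbAA, HbAS and HbSS.

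The cost is wording in sections 7.8 and 6.3, with no new participants, samples or images. Cross-validation needs more training runs: about 5 to 10 times as many with 5 to 10 folds and a single inner validation split, and more if it is nested over the candidate networks. Its estimate describes the training procedure rather than one fixed network, and its intervals are approximate because the folds share training data.

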# 3.0 Hypothesis

We hypothesize that

1. Gazelle diagnostic device can detect  $\beta$ -thalassemia and SCD/SCT with an overall accuracy greater than 90%, compared with HPLC as the reference test

- 2. an automated sickling test (standard sickling test enhanced using low-cost microscopy and machine learning) has a higher overall accuracy than conventional screening techniques (solubility and sickling tests) to detect hemoglobin S in blood samples
- 3. the automated sickling test can additionally classify SCD, SCT and healthy individuals with a sensitivity greater than 90%, based on morphology changes of red blood cells, unlike conventional sickling or solubility tests that do not distinguish between SCD and SCT cases

Overall, we hypothesize that an assessment of the performance and accuracies of low-cost point-of-care techniques (automated sickling test, solubility test, lateral-flow assays, Gazelle Hb variant test) against HPLC tests will provide researchers and health workers with feasible alternative options for screening and detecting SCD, SCT and  $\beta$ -thalassemia in a variety of situations based on the needs of the communities and the resources available.

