  - HbS Solubility: Not applicable, since solubility test can only identify the hemoglobin variant but not the homozygosity or heterozygosity

Any data that is excluded from the analysis, due to indeterminate results, missing data, withdrawal of consent, or any other reason, will be reported.

A total of around 120 participants – around 20 individuals with SCD (HbSS), 20 individuals with SCT (HbAS), 20 individuals with sickle cell /  $\beta$ -thalassemia compound heterozygous form (HbS/ $\beta$ -thalassemia), 20 individuals with  $\beta$ -thalassemia (Hb $\beta$ / $\beta$ -thalassemia), 20 individuals with  $\beta$ -thalassemia trait or carrier form (HbA/ $\beta$ -thalassemia), and 20 healthy individual participants (HbAA) – will be recruited for the study.

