# 12. Feasibility

Approximately 800 patients with SCA have been identified at Bheri Hospital and Mount Sagarmatha Polyclinic, and more with participants with sickle cell trait or  $\beta$ -thalassemia forms have been identified. Since the Bheri Hospital and Mount Sagarmatha Polyclinic are have HPLC machines, most patients from Nepalgunj and neighboring areas come to the hospital for diagnosis. Since Bheri hospital provides the diagnosis for free for SCD patients, the HPLC machine is relatively busy. The HPLC machine at Mount Sagarmatha Polyclinic is not as busy as that in Bheri hospital, which makes it more feasible to run the study at Mount Sagarmatha Polyclinic.

The hospital/clinic keeps a record of all patients, their diagnoses, and their contact information. As the number for each participant category is relatively small (i.e. 20 participants for each category), recruitment is feasible. We do not feel that additional participation in this study would be burdensome to patients and staff. We also plan to only recruit 20 healthy volunteers. We expect our recruitment efforts will assist in achieving this number.

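### The automated sickling test is evaluated on a single 10% split of images, so its test set is either independent but about 12 people, or larger but shared with training

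*Combined protocol and SAP*

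**What the plan says.** Section 7.8 states that "the acquired images will be split into three groups", "consisting of training data (around 80%), validation data, (around 10%) and testing data (around 10"%). It adds: "The test data will test the performance of the trained network on images that have not been used for training". It mentions neither cross-validation nor repeated splitting. It does not say that all images of one participant stay together, how many images each participant gives, or how image results become one result per participant.

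Section 5.0 puts the sensitivity and specificity of the automated sickling test, against HPLC, in the primary outcome. Section 6.3 scores it with the same TP/TN/FP/FN metrics as the other index tests, by variant and by phenotype ("Automated sickling: HbAA, HbAS, HbSS, Overall"), and gives no denominator for any test. The sample is "A total of around 120 participants" in six groups, with "20 participants for each category" (section 12).

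Two hypotheses in section 3.0 depend on this test. Hypothesis 2 says that it "has a higher overall accuracy than conventional screening techniques (solubility and sickling tests") for detecting HbS. Hypothesis 3 says that it can "classify SCD, SCT and healthy individuals with a sensitivity greater than 90"%. No interval method, test or significance level is given for either. Manual sickling is planned in sections 6.1 and 7.5.1 and is a comparator in Hypothesis 2, but section 6.3 does not list it as an index test.

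**The concern.** Solubility needs no training, so nothing in the plan keeps it from being scored on everyone. The automated test gives out-of-sample results only for the test portion of one split. A reader of section 6.3 would take the two sets of figures as equally well supported.

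The stake is a primary-outcome estimate that means little under either reading of the split. Divided by participant, the test set is too small to separate a good classifier from a mediocre one. Divided by image, the network is tested largely on blood films from people it has already seen, and part of the apparent accuracy may come from recognising a participant's slide rather than a phenotype.

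**Working it through.** **Inputs.** Six groups of 20 (sections 6.3, 7.2.1 and 12): 6 × 20 = 120, which reproduces the plan's total. HbS-positive groups are HbSS, HbAS and HbS/β-thalassemia (60 people); the other three are HbS-negative (60). Split 80/10/10 (section 7.8). Comparator accuracy from the ranges in section 1.5. Assumed, because the plan does not state them: two-sided 5% level, exact methods, no exclusions, independent errors between tests, automated-test accuracy of 95%, and the number of images per participant.

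**Reading A: split by participant.** 0.10 × 120 = 12 people; on average 0.10 × 20 = 2 per group and 0.10 × 60 = 6 HbS-positive.

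*Precision.* When all n results are correct, the exact 95% lower limit is 0.025^(1/n).

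| Correct | Lower limit |
|---|---|
| 2/2 | 15.8% |
| 6/6 | 54.1% |
| 12/12 | 73.5% |
| 20/20 | 83.2% |
| 60/60 | 94.0% |

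*Reading the 90% bar as a point estimate.* With 2 per class the only possible values are 0, 50 and 100%, so passing means 2/2. If true sensitivity is 80% in each of HbAA, HbAS and HbSS, all three pass with probability 0.8^6 = 0.26. With 20 per class, passing means at least 19/20, which has probability 0.069 per class and 0.069³ = 0.0003 for all three.

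*Empty classes.* The average of 2 per group is secured only by stratification. In an unstratified draw of 12, a given group is absent with probability C(100,12)/C(120,12) = 0.0996. At least one of HbAA, HbAS and HbSS is absent with probability 3(0.0996) − 3(0.0057) + 0.0001 = 0.28.

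*Hypothesis 2.* At a 60/60 mix, the low ends of the section 1.5 ranges give overall accuracy (45 + 90)/2 = 67.5% for solubility and (65 + 96)/2 = 80.5% for manual sickling. The high ends give 99.5% (rounded) and 98.5% (rounded). With the automated test at 95%, the discordant probabilities are:

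- against solubility at 67.5%: 0.95 × 0.325 = 0.309 in favour, 0.675 × 0.05 = 0.034 against;
- against manual sickling at 80.5%: 0.95 × 0.195 = 0.185 in favour, 0.805 × 0.05 = 0.040 against.

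An exact McNemar test needs at least six discordant pairs (6–0 gives p = 0.031; 5–0 gives 0.0625). Its power is:

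| Comparator | 12 pairs | 120 pairs |
|---|---|---|
| Solubility, 67.5% | 10% | over 99.9% |
| Manual sickling, 80.5% | 1% | 92% |
| Either, top of range | about 0 | about 0 |

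**Reading B: split by image, as literally written.** With k images per participant, the expected number of people with at least one test image is 120 × (1 − 0.9^k): 12 at k = 1, 49 at k = 5, 78 at k = 10 and 105 at k = 20. At k = 10 the chance that a participant has no training image is 0.2^10, about 1 in 10 million. Practically everyone in the test set is therefore also in the training set.

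**After cross-validation.** There are 120 out-of-fold results, 20 per group. A perfect 20/20 still has a lower limit of 83.2%. Excluding 90% with every result correct needs 0.9^n ≤ 0.025, so n = 36 per phenotype (29 at a one-sided 5% level).

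**The case against.** Four objections deserve an answer.

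First, a reader might infer that the plan fixes a test set of 12 people with 2 per phenotype. It does not. Section 7.8 divides images and is silent on participants and on stratification. That objection stands, and the figure of 12 is conditional here. It does not rescue the plan, because the alternative reading gains people only by losing independence.

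Second, a reader might infer that the automated test and solubility would be judged on different people. The documents do not support that: held-out participants are a subset of those with solubility results, and a paired comparison on that subset is possible. The difficulty is its size. Nor does the plan state that every comparator uses all 120. That is a natural inference for solubility, but for manual sickling section 6.3 specifies no analysis at all.

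Third, the outcome is worded as characterising accuracy, training the algorithm is a secondary outcome, and section 7.8 says the algorithm will not diagnose new patients. The plan sets no formal test, so the 5% McNemar test is imported here. This is fair. But a characterisation with a lower limit of 15.8% or 54.1% informs little, and Hypotheses 2 and 3 are comparative and threshold claims in the plan's own words.

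Fourth, a hold-out evaluates one frozen network, which cross-validation does not. That is a real loss, but a small one beside a test set of 12.

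**Conclusion.** The concern holds in conditional form. One 10% test portion gives either an independent evaluation on about 12 people or a larger one that shares participants with training; neither can support Hypotheses 2 and 3. Of the two, the image-level reading is closer to the text, and its likely effect is optimism. Its size cannot be calculated from the documents.

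It would be tempting to conclude that cross-validation settles both hypotheses. It does not. It makes Hypothesis 2 decidable only if the comparators perform near the low end of the section 1.5 ranges; at the top of those ranges power stays near zero with 120 pairs. For Hypothesis 3, the group size of 20 is itself a limit: no result at 20 per phenotype can exclude 90%.

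The power figures rest on 95% accuracy for the automated test, independent errors, a 60/60 mix and no exclusions. The participant counts under an image-level split rest on the assumed images per person. The exact lower limits rest only on the counts and the 95% level.

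**What to change.** In section 7.8, replace the single split with 10-fold cross-validation grouped by participant and stratified by phenotype, with all tuning and network selection inside the training folds. Fix in advance the rule that turns a participant's image results into one out-of-fold call.

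In section 6.3:

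- compute the metrics for the automated test on all 120 calls, with exact 95% intervals and the denominator stated;
- specify a paired comparison for Hypothesis 2 on those same people;
- add manual sickling to the index tests, because Hypothesis 2 names it;
- state how the three β-thalassemia groups (60 people) are scored for this test, since its phenotype list covers only HbAA, HbAS and HbSS;
- present Hypothesis 3 as estimation with exact intervals.

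The cost is wording in two sections and about ten times the training runs, on computing that section 7.8 already provides. No extra participants or blood are needed, and section 8.0 places the analysis after image collection. The drawback is that the accuracy reported describes the training procedure averaged over folds, not one frozen network; the report should say so.
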